## 6.3 Dose modifications for toxicities

### 6.3.1 Dose modification and dose interruption

For participants who do not tolerate the protocol-specified dosing schedule due to drug related toxicities, dose interruptions and/or reductions are recommended in order to allow participants to continue the study treatment. For the dose escalation part of the study, dose reductions during cycle 1 are only allowed if a DLT is observed and recorded.

Table 6-7 provides recommendations for dose modification and dose interruption (i.e., interruption and re-initiation criteria for nazartinib and capmatinib treatment).

Refer to Table 6-5 and Table 6-6 for recommended dose reduction steps for the Phase II part of the study.

If, due to study drug related toxicity, a participant requires a dose interruption of >21 days from the intended day of the next scheduled dose, then the participant must be discontinued from the study treatment unless described otherwise.

Each participant is only allowed two dose reductions on each drug. In addition, a participant must discontinue treatment with nazartinib and capmatinib if, after treatment is resumed at a lower dose, the toxicity recurs with the same or worse severity.

Exceptions on dose interruptions and modifications can be made on a case by case basis after discussion with Novartis and Investigator.

In exceptional cases, after discussion with Novartis, participants may be allowed to continue treatment or resume treatment with only one of the investigational drugs.

All dose interruptions or modifications must be recorded on the Dosage Administration Record CRF.

In case of study treatment interruption, visit schedule should still be followed and assessments performed as per Table 7-1 and Table 7-2.

After dose modification, re-escalation to a previous dose level is not permitted apart from the exceptional cases described in Table 6-14 and Table 6-15.

Events not included in the study protocol or the reference guidance documents should be managed according to local practices.

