**Table 6-6 Dose Reduction steps for nazartinib**

Dose level	Proposed daily dose of nazartinib
0	nazartinib 100 mg q.d.
-1	nazartinib 75 mg q.d.
-2	nazartinib 50 mg q.d.

Note: dose reduction should be based on the worst toxicity demonstrated at the last dose

**Table 6-7 Criteria for dose reduction, interruption and re-initiation of nazartinib and capmatinib for adverse drug reaction**

Worst toxicity CTCAEa Grade (value)	Recommendation
HEMATOLOGICAL	
Neutrophil count decreased (ANC) Neutropenia	
Grade 1 (ANC < LLN - 1500/mm  ; < LLN - 1.5 x 10  /L)	Maintain dose levels of nazartinib and capmatinib
Grade 2 (ANC < 1500 - 1000/mm  ; < 1.5 - 1.0 x 10  /L)	Maintain dose levels of nazartinib and capmatinib
Grade 3 (ANC <1000 – 500/mm  )	
Omit study treatment until resolved to ≤ grade 2, then resume nazartinib at the same dose level:
 
 
• If fully resolved in ≤ 7 days, then resume capmatinib at same dose level
 
• If fully resolved in > 7 days, then resume capmatinib at ↓ 1 dose level
 
• If recurrence of grade 3 toxicity on maintained dose of nazartinib and ↓ 1 dose level of capmatinib, omit study treatment until resolved to ≤ grade 2, then resume nazartinib at ↓ 1 dose level and the same dose level of capmatinib (i.e., both study drugs ↓ 1 dose level from dose levels at initial occurrence of grade 3 AE)
 
• If recurrence of grade 3 during nazartinib monotherapy, omit study treatment until resolved to ≤ grade 2, then resume nazartinib at ↓ 1 dose level
 
• If no recurrence of grade 3 toxicity after 7 days of nazartinib monotherapy at ↓ 1 dose level, resume capmatinib at same dose level
 

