Grade 4 (ANC < 500/mm  )	
Omit study treatment until resolved, then resume nazartinib at the same dose level
 
 
• If no recurrence of grade 3 or higher toxicity after 7 days of nazartinib monotherapy, resume capmatinib at ↓ 1 dose level
 
• If recurrence of grade 3 or higher toxicity on maintained dose level of nazartinib and ↓ 1 dose level of capmatinib, omit study treatment until resolved to ≤ grade 2, then resume nazartinib at ↓ 1 dose level and capmatinib at the same dose level (i.e., both study drugs ↓ 1 dose level from levels at initial occurrence of grade 4 AE)
 
• If recurrence of grade 3 or higher toxicity during nazartinib monotherapy, omit study treatment until resolved to ≤ grade 2, then resume nazartinib at ↓ 1 dose level
 
• If no recurrence of grade 4 toxicity after 7 days of nazartinib monotherapy at ↓ 1 dose level, resume capmatinib at the same dose level
 

Febrile Neutropenia	
ANC < 1000/mm  and a single temperature of >38.3°C (101°F) or a sustained temperature of ≥38°C (100.4°F) for more than one hour	
Omit study treatment until resolved, then resume nazartinib at the same dose level:
 
 
• If resolved in ≤ 7 days, resume capmatinib treatment at ↓ 1 dose level
 
• If resolved in > 7 days, permanently discontinue capmatinib treatment
 
• If recurrence during nazartinib monotherapy, omit nazartinib until resolved, then resume nazartinib ↓ 1 dose level and capmatinib at ↓ 1 dose level
 

Platelet count decreased (Thrombocytopenia)	
Grade 1 (PLT < LLN - 75,000/mm  ; < LLN - 75 x 10  /L)	Maintain dose levels of nazartinib and capmatinib
Grade 2 (PLT < 75,000 - 50,000/mm  ; < 75 - 50 x 10  /L)	Maintain dose levels of nazartinib and capmatinib
Grade 3 (PLT < 50,000 - 25,000/mm  )	Omit study treatment until resolved to ≤ grade 2, then resume nazartinib at the same dose level:

Worst toxicity CTCAE a Grade (value)	Recommendation

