Grade ≥3	Omit study treatment until resolved to ≤ grade 1, then resume nazartinib at same dose level of and re-evaluate after 7 days, or sooner if clinically indicated 
 
• If no recurrence of grade 3 toxicity after 7 days of nazartinib monotherapy, resume capmatinib at ↓ 1 dose level
 
• If recurrence of grade 3 toxicity on maintained dose level of nazartinib and ↓ 1 dose level of capmatinib, omit study treatment until resolved to ≤ grade 1, then resume nazartinib at ↓ 1 dose level and maintain dose level of capmatinib (i.e., both study drugs ↓ 1 dose level from levels at initial occurrence of grade 3 AE)
 
• If recurrence of grade 3 toxicity during nazartinib monotherapy, omit study treatment until resolved to ≤ grade 1, then nazartinib at ↓ 1 dose level
 
• If no recurrence of grade 3 toxicity after 7 days of nazartinib monotherapy at ↓ 1 dose level, resume capmatinib at ↓ 1 dose level
 

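### Section 6.3.1 requires both drugs to stop when a toxicity recurs after resumption at a lower dose, but Table 6-7 resumes both after such a recurrence: outright in four rows, conditionally in three

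*Protocol*

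**What the plan says.** The general rule in Protocol Section 6.3.1 is that a participant "must discontinue treatment with nazartinib and capmatinib if, after treatment is resumed at a lower dose, the toxicity recurs"; it is limited to recurrences of equal or greater severity. The sentence before it reads "Each participant is only allowed two dose reductions on each drug". The section introduces the table as follows: "Table 6-7 provides recommendations for dose modification and dose interruption". It also carries an exception clause: "Exceptions on dose interruptions and modifications can be made on a case by case basis after discussion with Novartis and Investigator".

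Table 6-7 covers the combination. Seven of its rows have a branch for toxicity that recurs while nazartinib is at its unchanged dose and capmatinib has been lowered by one level. In each, treatment is withheld until the event resolves and both drugs are then given again. The grade 3 neutropenia row describes the result as "both study drugs ↓ 1 dose level from dose levels at initial occurrence of grade 3 AE", and the row for other adverse events of grade 3 or more as "both study drugs ↓ 1 dose level from levels at initial occurrence of grade 3 AE".

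Two other rows of Table 6-7 matter. Vomiting has a row for grade 3 and above (withhold, then resume) and a separate grade 4 row (discontinue). Febrile neutropenia has a bullet for recurrence on nazartinib alone: "then resume nazartinib ↓ 1 dose level and capmatinib at ↓ 1 dose level". The same row stops capmatinib permanently if resolution takes more than 7 days.

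**The concern.** A mandatory stopping rule and the table meant to apply it give different instructions for the same event. Two sites, each following the protocol, could treat the same participant differently after a recurrent grade 3 toxicity: one stops both drugs and the other restarts both.

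The direct stake is participant safety. The statistical stake is consistency of the tolerability data. Table 3-1 lists dose interruptions, reductions and dose intensity as Group 5 tolerability endpoints, and the objective covers the combination as well as capmatinib alone. If sites resolve the conflict differently, those summaries partly reflect which text a site followed.

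**Working it through.** No formula or sample size is involved. The check sets the Section 6.3.1 rule against every Table 6-7 row.

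**The test.** The rule applies when (a) treatment was resumed at a lower dose and (b) the recurrence is of the same or worse severity. A row conflicts if it tells the site to resume both drugs when both conditions hold.

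| Table 6-7 row | Recurrence that triggers the branch | Action after resolution | Against Section 6.3.1 |
|---|---|---|---|
| Neutropenia grade 3 | grade 3 | nazartinib one level down, capmatinib stays at the reduced level | outright |
| Serum creatinine grade 3 | grade 3 | nazartinib unchanged, capmatinib one level down | outright |
| Isolated bilirubin grade 3 | grade 3 | nazartinib unchanged, capmatinib one level down | outright |
| Peripheral edema grade 3 | grade 3 | nazartinib unchanged, capmatinib one level down | outright |
| Neutropenia grade 4 | grade 3 or higher | nazartinib one level down, capmatinib stays at the reduced level | only if the recurrence is grade 4 |
| Thrombocytopenia grade 4 | grade 3 or higher | nazartinib one level down, capmatinib stays at the reduced level | only if the recurrence is grade 4 |
| Other adverse events grade 3 or more | grade 3 | nazartinib one level down, capmatinib stays at the reduced level | only if the initial event was grade 3 |

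Count: 4 outright + 3 conditional = 7 rows. The three are conditional because a grade 3 recurrence after a grade 4 event is less severe, so the rule does not reach it.

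**Rows not counted.** Grade 3 platelets, anemia, AST/ALT, nausea and fatigue, for example, mention recurrence only while nazartinib is given alone at an unchanged dose. Condition (a) is not clearly met there.

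**Does anything in Section 6.3.1 settle it?** The words allowing for a different description elsewhere belong to the sentence on interruptions longer than 21 days, not to the recurrence sentence. The exception clause is for individual cases after discussion, so it does not cover standing table instructions. The limit of two reductions per drug is compatible with either text, since a second reduction can follow a different toxicity.

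**Vomiting.** A grade 4 event meets the label of the grade 3-and-above row and that of the grade 4 row. The actions differ.

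**Febrile neutropenia.** Once capmatinib is permanently stopped and nazartinib continues alone, Table 6-9 applies by its own title. It has its own febrile neutropenia row, with no capmatinib instruction. What remains is that the Table 6-7 bullet does not say which period of nazartinib alone it means.

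**Reach.** The Amendment 07 rationale states that no participant in Phase Ib or Groups 1 to 4 is still on treatment. Group 5 starts on capmatinib alone, for which Table 6-8 applies, and may add nazartinib after progression (Section 6.1.2). Table 6-7 therefore matters for those who enter that stage, and this conflict for those among them whose toxicity recurs at a reduced dose. Group 5 plans about 30 participants; how many would meet these conditions is not given.

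**The case against.** The strongest defence is that the two texts can be read together. Section 6.1 defines study treatment as the combination, so resuming treatment at a lower dose could mean that both drugs have been lowered. All seven branches start with nazartinib at its unchanged dose. Four of them (both neutropenia rows, grade 4 thrombocytopenia and other adverse events) end with both drugs one level down and give no branch for a further recurrence on the combination. Section 6.3.1 could take over at that point. The reading is possible, but the protocol does not state it, and Section 6.3.1 counts reductions drug by drug. The creatinine, bilirubin and edema branches leave nazartinib unlowered, so on this reading the rule would not yet apply there, and nothing says so.

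A second defence is that the table only recommends. That does not remove the problem, because following the recommendation would still breach a mandatory sentence.

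Other objections stand and limit the point. A reader might infer that seven rows, or every row that mentions recurrence, contradict the rule; only four do so unconditionally. A reader might take febrile neutropenia as a second internal contradiction; Table 6-9 largely answers that. For grade 4 vomiting, the more specific row is the natural one to follow, though the labels still overlap.

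**Conclusion.** The inconsistency is real and should be corrected, within these limits. Four Table 6-7 rows conflict with Section 6.3.1 outright and three under stated conditions, and one further row pair (vomiting) overlaps at grade 4. The febrile neutropenia bullet is unclear rather than contradictory.

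Three wider inferences are not supported. It would be wrong to say that no rule governs discontinuation: Table 6-7 fixes it clearly elsewhere, for example for grade 4 bilirubin, grade 4 AST/ALT and grade 3 or 4 pneumonitis. The gap concerns recurrence at a reduced dose. Discontinuation rate and exposure are not named as Group 5 endpoints in Table 3-1. The primary response rate is not affected, because it is measured on capmatinib monotherapy.

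The conclusion rests on two assumptions: that lowering one drug counts as resuming at a lower dose, which the text neither says nor excludes, and that no order of precedence is given in protocol text beyond the part reviewed, which ends at the start of Section 6.3.2.

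**What to change.** Reconcile Section 6.3.1 with Table 6-7. State which text governs recurrence at a reduced dose, and whether a lower dose means either drug or both. Then make the seven rows agree with that statement, including the severity condition in the three conditional rows. Relabel the vomiting rows so that grade 4 has one action. In the febrile neutropenia row, say which period of nazartinib alone the recurrence bullet means, and cross-refer to Table 6-9 where capmatinib has been permanently stopped.

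The clinical team decides the content of each rule; this point asks only that the texts agree. The cost is protocol wording and a clarification to sites, with no change to design, sample size or analysis.

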**Table 6-5 Dose reduction steps for capmatinib**

Dose level	Proposed daily dose of capmatinib
0	capmatinib 400 mg b.i.d.
-1	capmatinib 300 mg b.i.d.
-2	capmatinib 200 mg b.i.d.

**Table 6-6 Dose Reduction steps for nazartinib**

Dose level	Proposed daily dose of nazartinib
0	nazartinib 100 mg q.d.
-1	nazartinib 75 mg q.d.
-2	nazartinib 50 mg q.d.

Note: dose reduction should be based on the worst toxicity demonstrated at the last dose

**Table 6-7 Criteria for dose reduction, interruption and re-initiation of nazartinib and capmatinib for adverse drug reaction**

Worst toxicity CTCAEa Grade (value)	Recommendation
HEMATOLOGICAL	
Neutrophil count decreased (ANC) Neutropenia	
Grade 1 (ANC < LLN - 1500/mm  ; < LLN - 1.5 x 10  /L)	Maintain dose levels of nazartinib and capmatinib
Grade 2 (ANC < 1500 - 1000/mm  ; < 1.5 - 1.0 x 10  /L)	Maintain dose levels of nazartinib and capmatinib
Grade 3 (ANC <1000 – 500/mm  )	
Omit study treatment until resolved to ≤ grade 2, then resume nazartinib at the same dose level:
 
 
• If fully resolved in ≤ 7 days, then resume capmatinib at same dose level
 
• If fully resolved in > 7 days, then resume capmatinib at ↓ 1 dose level
 
• If recurrence of grade 3 toxicity on maintained dose of nazartinib and ↓ 1 dose level of capmatinib, omit study treatment until resolved to ≤ grade 2, then resume nazartinib at ↓ 1 dose level and the same dose level of capmatinib (i.e., both study drugs ↓ 1 dose level from dose levels at initial occurrence of grade 3 AE)
 
• If recurrence of grade 3 during nazartinib monotherapy, omit study treatment until resolved to ≤ grade 2, then resume nazartinib at ↓ 1 dose level
 
• If no recurrence of grade 3 toxicity after 7 days of nazartinib monotherapy at ↓ 1 dose level, resume capmatinib at same dose level
 

Grade 4 (ANC < 500/mm  )	
Omit study treatment until resolved, then resume nazartinib at the same dose level
 
 
• If no recurrence of grade 3 or higher toxicity after 7 days of nazartinib monotherapy, resume capmatinib at ↓ 1 dose level
 
• If recurrence of grade 3 or higher toxicity on maintained dose level of nazartinib and ↓ 1 dose level of capmatinib, omit study treatment until resolved to ≤ grade 2, then resume nazartinib at ↓ 1 dose level and capmatinib at the same dose level (i.e., both study drugs ↓ 1 dose level from levels at initial occurrence of grade 4 AE)
 
• If recurrence of grade 3 or higher toxicity during nazartinib monotherapy, omit study treatment until resolved to ≤ grade 2, then resume nazartinib at ↓ 1 dose level
 
• If no recurrence of grade 4 toxicity after 7 days of nazartinib monotherapy at ↓ 1 dose level, resume capmatinib at the same dose level
 

Febrile Neutropenia	
ANC < 1000/mm  and a single temperature of >38.3°C (101°F) or a sustained temperature of ≥38°C (100.4°F) for more than one hour	
Omit study treatment until resolved, then resume nazartinib at the same dose level:
 
 
• If resolved in ≤ 7 days, resume capmatinib treatment at ↓ 1 dose level
 
• If resolved in > 7 days, permanently discontinue capmatinib treatment
 
• If recurrence during nazartinib monotherapy, omit nazartinib until resolved, then resume nazartinib ↓ 1 dose level and capmatinib at ↓ 1 dose level
 

Platelet count decreased (Thrombocytopenia)	
Grade 1 (PLT < LLN - 75,000/mm  ; < LLN - 75 x 10  /L)	Maintain dose levels of nazartinib and capmatinib
Grade 2 (PLT < 75,000 - 50,000/mm  ; < 75 - 50 x 10  /L)	Maintain dose levels of nazartinib and capmatinib
Grade 3 (PLT < 50,000 - 25,000/mm  )	Omit study treatment until resolved to ≤ grade 2, then resume nazartinib at the same dose level:

Worst toxicity CTCAE a Grade (value)	Recommendation
	
 
• If fully resolved in ≤ 7 days, then resume capmatinib at same dose level
 
• If fully resolved in > 7 days, then resume capmatinib ↓ 1 dose level
 
• If recurrence of grade 3 toxicity during nazartinib monotherapy, omit study treatment until resolved to ≤ grade 2, then resume nazartinib ↓ 1 dose level, resume capmatinib at same dose level
 

Grade 4 (PLT < 25,000/mm  )	
Omit study treatment until resolved to ≤ grade 2, then resume nazartinib at the same dose level:
 
 
• If no recurrence of grade 3 or higher toxicity after 7 days of nazartinib monotherapy, resume capmatinib at ↓ 1 dose level
 
• If recurrence of grade 3 or higher toxicity on maintained dose of nazartinib and ↓ 1 dose level of capmatinib, omit study treatment until resolved to ≤ grade 2, then ↓ 1 dose level of nazartinib and maintain dose level of capmatinib (i.e., both study drugs ↓ 1 dose level from dose levels at initial occurrence of grade 4 AE)
 
• If recurrence of grade 3 or higher toxicity during nazartinib monotherapy, omit study treatment until resolved to ≤ grade 2, then resume nazartinib ↓ 1 dose level
 
• If no recurrence of grade 3 or higher toxicity after 7 days of nazartinib monotherapy at ↓ 1 dose level, resume capmatinib at ↓ 1 dose level
 

Hemoglobin decreased (Anemia)	
Grade 1 (Hgb < LLN - 10.0 g/dL; < LLN - 6.2 mmol/L; < LLN - 100 g/L)	Maintain dose levels of nazartinib and capmatinib
Grade 2 (Hgb < 10.0 - 8.0 g/dL; < 6.2 - 4.9 mmol/L; < 100 - 80 g/L)	Maintain dose level of nazartinib and capmatinib
Grade 3 (Hgb < 8 g/dL)	
Omit study treatment until resolved to ≤ grade 2, then resume at same dose levels of nazartinib:
 
 
• If fully resolved in ≤ 7 days, then resume capmatinib at same dose level
 
• If fully resolved in > 7 days, then resume capmatinib at ↓ 1 dose level
 
• If recurrence of grade 3 toxicity during nazartinib monotherapy, omit study treatment until resolved to ≤ grade 2, then resume nazartinib ↓ 1 dose level and resume capmatinib at same dose level
 

Grade 4 (life-threatening consequences; urgent intervention indicated)	
Omit study treatment until resolved to ≤ grade 2, then resume same dose level of nazartinib and re-evaluate in 7 days, or sooner if clinically indicated
 
 
• If no recurrence of grade 3 or higher toxicity after 7 days of nazartinib monotherapy, resume capmatinib at ↓ 1 dose level
 
• If recurrence of grade 3 or higher toxicity during nazartinib monotherapy, omit study treatment until resolved to ≤ grade 2, then resume at ↓ 1 dose level of nazartinib.
 
• If no recurrence of grade 3 or higher toxicity after 7 days of nazartinib monotherapy at ↓ 1 dose level, resume capmatinib at ↓ 1 dose level
 

RENAL	
Serum creatinine	
Grade 1 (> ULN - 1.5 x ULN)	Maintain dose levels of nazartinib and capmatinib
Grade 2 (> 1.5 and ≤ 3.0 x baseline; or > 1.5 and ≤ 3 x ULN)	Omit study treatment until resolved to ≤ grade 1 or baseline, then resume treatment at the same dose level of nazartinib and capmatinib
Grade 3 (> 3.0 x baseline; or > 3.0 and ≤ 6.0 x ULN)	Omit study treatment until resolved to ≤ grade 1, then resume nazartinib at the same dose level:

Worst toxicity CTCAE a Grade (value)	Recommendation
	
 
• If no recurrence of grade 3 toxicity after 7 days of nazartinib monotherapy, resume capmatinib at ↓ 1 dose level
 
• If recurrence of grade 3 toxicity on maintained dose of nazartinib and ↓ 1 dose level of capmatinib, omit study treatment until resolved to ≤ grade 1, then resume nazartinib at same dose level and Capmatinib ↓ 1 dose level
 
• If recurrence of grade 3 toxicity during nazartinib monotherapy, omit study treatment until resolved to ≤ grade 1 or baseline, then resume nazartinib ↓ 1 dose level
 
• If no recurrence of grade 3 toxicity after 7 days of nazartinib monotherapy at ↓ 1 dose level, resume capmatinib at ↓ 1 dose level
 

Grade 4 (> 6.0 × ULN)	Discontinue capmatinib permanently and omit nazartinib until resolved to ≤ grade 1 or baseline, then resume nazartinib at same dose level.
HEPATICb	
Isolated Total Bilirubin elevation (for participants with Gilbert Syndrome these dose modifications apply to changes in direct [conjugated] bilirubin only)	
Grade 1 (> ULN – 1.5 × ULN)	Maintain nazartinib and capmatinib dose level
Grade 2 (> 1.5 and ≤ 3.0 × ULN)	Omit study treatment. Monitor LFTs c weekly, or more frequently if clinically indicated until resolved to ≤ grade 1, then resume nazartinib and capmatinib at the same dose level.
Grade 3 (> 3.0 and ≤ 10.0 × ULN) g	
Omit study treatment. Monitor LFTsc weekly, or more frequently if clinically indicated until resolved to ≤ grade 1, then resume nazartinib at the same dose level.
 
 
• If no recurrence of grade 3 toxicity after 7 days of nazartinib monotherapy, resume capmatinib at ↓ 1 dose level
 
• If recurrence of grade 3 toxicity on maintained dose level of nazartinib and ↓ 1 dose level of capmatinib, omit study treatment until resolved to ≤ grade 1, then resume nazartinib at same dose level and Capmatinib ↓ 1 dose level
 
• If recurrence of grade 3 toxicity during nazartinib monotherapy, omit study treatment until resolved to ≤ grade 1, then resume nazartinib at ↓ 1 dose level
 
• If no recurrence of grade 3 toxicity after 7 days of nazartinib monotherapy at ↓ 1 dose level, resume capmatinib at ↓ 1 dose level
 

Grade 4 (> 10.0 × ULN) g	
Discontinue participant permanently from capmatinib and nazartinib.
 
The participant should be monitored weekly (including LFTsc), or more frequently if clinically indicated, until total bilirubin has resolved to baseline or stabilization over 4 weeks.

Isolated AST or ALT elevation	
Grade 2 (> 3.0 and ≤ 5.0 × ULN)	
Maintain dose level of both drugs with LFTsc monitored per protocol.
 
Repeat LFTsc as soon as possible, preferably within 48-72 hours from awareness of the abnormal results; if abnormal lab values are confirmed upon the repeat test, then monitor LFTsc weekly, or more frequently if clinically indicated, until resolved to ≤ grade 1.

Grade 3 (> 5.0 - 20.0 × ULN)	
Omit study treatment. Monitor LFTsc weekly, or more frequently if clinically indicated until resolved to ≤ grade 1, then resume nazartinib at the same dose level:
 
 
• If resolved in ≤ 7 days, then resume capmatinib at same dose level
 
• If resolved in > 7 days, then resume capmatinib at ↓ 1 dose level
 
• If recurrence during nazartinib monotherapy, omit study treatment until resolved to ≤ grade 1, then resume nazartinib at ↓ 1 dose level
 
• If no recurrence after 7 days of nazartinib monotherapy at ↓ 1 dose level, then resume capmatinib at ↓ 1 dose level
 

Grade 4 (> 20.0 × ULN)	Mandatory: Permanently discontinue both study drugs.

Worst toxicity CTCAE a Grade (value)	Recommendation
	Repeat LFTs c as soon as possible, preferably within 48-72 hours from awareness of the abnormal results; monitor LFTs c weekly, or more frequently if clinically indicated, until resolved to baseline or stabilization over 4 weeks.
Combinedd elevations of AST or ALT and concurrent Total bilirubinf	

For participants with normal baseline ALT and AST and total bilirubin value: AST or ALT > 3.0 × ULN combined with total bilirubin > 2.0 × ULN without evidence of cholestasise
 
or
 
For participants with elevated baseline AST or ALT or total bilirubin value: [AST or ALT > 3x baseline or [AST or ALT > 8.0 × ULN], whichever is lower, combined with [total bilirubin >2x baseline AND >2.0 × ULN]
	
Permanently discontinue nazartinib and capmatinib in the absence of signs of cholestasis, hemolysis, and if alternative causes of the liver injury have been excluded (e.g., concomitant use of hepatotoxic drug(s), alcoholic hepatitis, viral hepatitis etc.) Repeat LFTsc as soon as possible, preferably within 48 hours from awareness of the abnormal results, then with weekly monitoring of LFTsb, or more frequently if clinically indicated, until AST, ALT, or bilirubin have resolved to baseline or stabilized over 4 weeks.

METABOLICh	
Amylase and/or lipase elevation	
Grade 3 (>2.0 - 5.0 x ULN with signs or symptoms; >5.0 x ULN and asymptomatic)	
Omit study treatment until resolved to ≤ grade 1, then resume nazartinib at the same dose level:
 
 
• If resolved in ≤ 14 days, resume capmatinib at the same dose level
 
• If resolved in > 14 days, resume capmatinib at ↓ 1 dose level
 
• If recurrence of grade 3 toxicity during nazartinib monotherapy, omit study treatment until resolved to ≤ grade 2, then ↓ 1 dose level nazartinib
 
• If no recurrence of grade 3 toxicity after 7 days of nazartinib monotherapy at ↓ 1 dose level, resume capmatinib at ↓ 1 dose level
 

Grade 4 (>5.0 x ULN and with signs or symptoms)	Permanently discontinue capmatinib and omit nazartinib until resolved to grade ≤ 2, then maintain dose level of nazartinib. Monitor for recurrence of grade 3 toxicity after 7 days or sooner if clinically indicated

Note: Perform diagnostic procedures (e.g., abdominal CT scan or ultrasound) to exclude pancreatic pathology. Withhold study treatment for acute onset of new or progressive unexplained abdominal symptoms, such as severe pain or vomiting; if diagnosed with pancreatitis ≥ grade 3 permanently discontinue from capmatinib treatment.
	
HBV and HCV reactivation	
Refer to Table 6-10 , Table 6-11 and Table 6-12 , and Section 6.3.2 for details.	
CARDIAC	
Electrocardiogram QT corrected (QTc) interval prolonged	
Grade 3 (QTc ≥ 501 ms on at least two separate ECGs)	
Omit study treatment until resolved to ≤ grade 1 then:
 
 
• If resolved in ≤ 7 days, resume capmatinib at same dose level and nazartinib at ↓ 1 dose level
 
• If resolved in > 7 days, resume capmatinib and nazartinib at ↓ 1 dose level
 

Grade 4 ([QT/QTc ≥ 501 or > 60 ms change	Permanently discontinue nazartinib and capmatinib.

Worst toxicity CTCAEa Grade (value)	Recommendation
from baseline] and [Torsades de pointes or polymorphic ventricular tachycardia, or signs/symptoms of serious arrhythmia])	Obtain local cardiologist (or qualified specialist) consultation and repeat cardiac monitoring as indicated until the QTcF returns to <481 ms.
VASCULAR DISORDERS	
Hypertension CTCAE grade 3 for at least 7 days, despite treatment	
Omit nazartinib dose until resolved <math>\leq</math> grade 1, then maintain dose level of capmatinib and re-evaluate after 7 days, or sooner if clinically indicated
 
 
• If no recurrence of grade 3 toxicity after 7 days of capmatinib monotherapy, resume nazartinib at <math>\downarrow</math> 1 dose level
 
• If recurrence of grade 3 toxicity during capmatinib monotherapy, omit study treatment until resolved to <math>\leq</math> grade 1, then resume capmatinib <math>\downarrow</math> 1 dose level
 
• If no recurrence of grade 3 toxicity after 7 days of capmatinib monotherapy at <math>\downarrow</math> 1 dose level, resume nazartinib at <math>\downarrow</math> 1 dose level
 

CTCAE grade 4	Discontinue capmatinib and nazartinib
GASTROINTESTINAL	
Diarrheae	
Grade 1	Maintain dose levels of both study drugs but institute anti-diarrheal treatment
Grade 2 (despite maximal anti-diarrheal medication)	Omit dose until resolved to $\leq$ grade 1, then maintain dose levels of both study drugs.
Grade $\geq$ 3 (despite maximal anti-diarrheal medication)	
Omit study treatment until resolved to <math>\leq</math> grade 1, then resume capmatinib at same dose level
 
 
• If no recurrence of grade 3 toxicity after 7 days of capmatinib monotherapy, resume nazartinib at <math>\downarrow</math> 1 dose level
 
• If recurrence of grade 3 toxicity during capmatinib monotherapy, omit study treatment until resolved to <math>\leq</math> grade 1, then resume capmatinib <math>\downarrow</math> 1 dose level
 
• If no recurrence of grade 3 toxicity after 7 days of capmatinib monotherapy at <math>\downarrow</math> 1 dose level, resume nazartinib at same dose level
 

Dose modifications apply to participants who experience diarrhea despite appropriate anti-diarrheal medication. This medication should be started at the first sign of diarrhea.	
Nausea	
Grade 1 or 2	Maintain dose levels of both study drugs but adjust anti-emetic treatment
Grade $\geq$ 3 (despite standard anti-emetics)	
Omit study treatment until resolved to <math>\leq</math> grade 1, then resume nazartinib at same dose level
 
 
• If no recurrence of grade 3 toxicity after 7 days of nazartinib monotherapy, resume capmatinib at <math>\downarrow</math> 1 dose level
 
• If recurrence of grade 3 toxicity during nazartinib monotherapy, omit study treatment until resolved to <math>\leq</math> grade 1, then <math>\downarrow</math> 1 dose level capmatinib
 
• If no recurrence of grade 3 toxicity after 7 days of capmatinib monotherapy at <math>\downarrow</math> 1 dose level, resume nazartinib at same dose level
 

Vomiting	
Grade 1	Maintain dose levels of both study drugs but adjust anti-emetic treatment
Grade 2 (despite standard anti-emetics)	Omit study treatment until resolved to $\leq$ grade 1, then maintain dose levels of both drugs.
Grade $\geq$ 3 (despite standard anti-emetics)	Omit study treatment until resolved to $\leq$ grade 1, then resume nazartinib at same dose level

Worst toxicity CTCAEa Grade (value)	Recommendation
	
 
If no recurrence of grade 3 toxicity after 7 days of nazartinib monotherapy, resume capmatinib at ↓ 1 dose level
 
If recurrence of grade 3 toxicity during nazartinib monotherapy, omit study treatment until resolved to ≤ grade 1, then ↓ 1 dose level capmatinib
 
If no recurrence of grade 3 toxicity after 7 days of capmatinib monotherapy at ↓ 1 dose level, resume nazartinib at same dose level
 

Grade 4 (despite standard anti-emetics)	Discontinue study treatment
Dose modifications apply to participants who experience nausea and/or vomiting despite appropriate antiemetic medication. This medication should be started at the first sign of nausea and/or vomiting.	
SKIN AND SUBCUTANEOUS TISSUE DISORDERS	
Stevens-Johnson Syndrome (SJS) or Lyell syndrome/Toxic Epidermal Necrolysis (TEN)	Permanently discontinue study treatment and manage per institutional guidelines.
Rashl	
Grade 1 Macules/papules covering <10% BSA (Body Surface Area)	Maintain dose levels of nazartinib and capmatinib
Grade 2 Macules/papules covering 10 - 30% BSA	Maintain dose levels of nazartinib and capmatinib
Grade 3 Macules/papules covering >30% BSA	
Omit study treatment until resolved to ≤grade 1, then resume capmatinib at the same dose level.
 
 
If no recurrence of grade 3 toxicity after 7 days of capmatinib monotherapy, resume nazartinib at ↓ 1 dose level
 
If recurrence of grade 3 toxicity during capmatinib monotherapy, omit study treatment until resolved to ≤ grade 1, then resume capmatinib ↓ 1 dose level
 
If no recurrence of grade 3 toxicity after 7 days of capmatinib monotherapy at ↓ 1 dose level, resume nazartinib at same dose level
 

Grade 4	Permanently discontinue study treatment
RESPIRATORY, THORACIC AND MEDIASTINAL DISORDERS	
Pneumonitis/Interstitial lung disease	
Grade 1	
Interrupt study treatment during diagnostic workup for ILD/Pneumonitis. Exclude infections and other etiologies.
 
In presence of diagnosis of ILD/Pneumonitis after diagnostic workup, it is mandatory to permanently discontinue capmatinib and nazartinib.
 
Only in the absence of a diagnosis of ILD/Pneumonitis, capmatinib and nazartinib may be resumed at the same dose.
 
If it recurs after resumption of study drug, permanently discontinue capmatinib and nazartinib.

Grade 2	
Mandatory: Omit capmatinib and nazartinib during diagnostic workup for ILD/pneumonitis until improvement to ≤ Grade 1. Exclude infections and other etiologies.
 
In presence of diagnosis of ILD/Pneumonitis after diagnostic workup, it is mandatory to permanently discontinue capmatinib and nazartinib.
 
Only in the absence of a diagnosis of ILD/Pneumonitis, capmatinib and nazartinib may be resumed following these guidelines:
 
 
If resolves to ≤ Grade 1 in ≤ 7 days capmatinib and nazartinib at ↓1 dose level
 

Worst toxicity CTCAE a Grade (value)	Recommendation
	
 
If fails to resolve to ≤ Grade 1 within 7 days or recurs after resumption of capmatinib and nazartinib at ↓1 dose level , permanently discontinue capmatinib and nazartinib.
 

Grade 3 OR Grade 4	Permanently discontinue study treatment.
GENERAL DISORDERS AND ADMINISTRATION SITE CONDITIONS	
Fatigue/ Asthenia	
Grade 1 or 2	Maintain dose levels of nazartinib and capmatinib
Grade 3	
Omit study treatment until resolved to ≤ grade 1, then resume nazartinib at the same dose level:
 
 
If resolved in ≤ 7 days, then resume capmatinib at same dose level
 
If resolved in > 7 days, then resume capmatinib ↓ 1 dose level
 
If recurrence of grade 3 toxicity during nazartinib monotherapy, omit study treatment until resolved to ≤ grade 1, then resume nazartinib at ↓ 1 dose level
 
If no recurrence of grade 3 toxicity after 7 days of nazartinib monotherapy at ↓ 1 dose level, resume capmatinib at same dose level
 

Peripheral edema	
Grade 1 or 2	Maintain dose levels of nazartinib and capmatinib
Grade 3	
Omit study treatment until resolved to ≤ grade 1, then resume nazartinib at same dose level and re-evaluate after 7 days, or sooner if clinically indicated
 
 
If no recurrence of grade 3 toxicity after 7 days of nazartinib monotherapy, resume capmatinib at ↓ 1 dose level
 
If recurrence of grade 3 toxicity on maintained dose of nazartinib and ↓ 1 dose level of capmatinib, omit study treatment until resolved to ≤ grade 1, then resume capmatinib at ↓ 1 dose level and maintain dose level of nazartinib
 
If recurrence of grade 3 toxicity during nazartinib monotherapy, omit study treatment until resolved to ≤ grade 1, then resume nazartinib at ↓ 1 dose level
 
If no recurrence of grade 3 toxicity after 7 days of nazartinib monotherapy at ↓ 1 dose level, resume capmatinib at ↓ 1 dose level
 

Grade 4	Permanently discontinue capmatinib and omit dose of nazartinib until resolved to ≤ grade 1, then continue nazartinib monotherapy
Eye Disorders (Results and images of ophthalmic examinations should be made available upon request)	
Grade 1 or 2 Uveitis/Retinopathy	Maintain dose level of both study drugs, and refer to an ophthalmologist for ophthalmic monitoring at least every 14 days.
Grade 3 Uveitis/Retinopathy	
Omit study treatment until resolved to ≤ grade 1, and refer to an ophthalmologist for ophthalmic monitoring at least once a week, then:
 
 
If resolved in ≤ 14 days, then resume capmatinib at same dose level and nazartinib at ↓ 1 dose level
 
If resolved in > 14 days, then permanently discontinue participant from nazartinib and resume capmatinib at same dose level
 

Grade 4 Uveitis/Retinopathy	
Permanently discontinue nazartinib and refer the participant to an ophthalmologist for monitoring. Resumption of nazartinib following resolution to ≤ grade 1 may be considered if approved by ophthalmologist and after documented discussion with Novartis.
 
Resume capmatinib at same dose level upon resolution to ≤ grade 1.

Retinal vein occlusion of any Grade	Permanently discontinue nazartinib and refer the participant to an ophthalmologist immediately for monitoring. Resumption of nazartinib following resolution to ≤ grade

Worst toxicity CTCAE a Grade (value)	Recommendation
	1 may be considered may be considered if approved by ophthalmologist and after documented discussion with Novartis. Resume capmatinib at same dose level upon resolution to ≤ grade 1.
Other ocular/visual toxicity	
Grade 1 or 2	Maintain dose levels of both drugs, and within one week refer to an ophthalmologist for ophthalmic monitoring at least every 14 days.
Grade 3	Omit study treatments until resolved to ≤ grade 1, and within one week refer to an ophthalmologist for ophthalmic monitoring at least once a week, then: 
 
• If resolved in ≤ 14 days, then resume capmatinib at same dose level and nazartinib at ↓ 1 dose level
 
• If resolved in > 14 days, then discontinue participant from nazartinib and resume capmatinib ↓ 1 dose level
 

Grade 4	Permanently discontinue nazartinib, omit capmatinib and refer the participant to an ophthalmologist immediately for monitoring. Resumption of nazartinib at ↓ 1 dose level following resolution to ≤ grade 1 may be considered if approved by ophthalmologist and after documented discussion with Novartis. Resume capmatinib at same dose level upon resolution to ≤ grade 1.
Other adverse events	
Grade 1 or 2	Maintain dose levels of nazartinib and capmatinib
